8.2.2 Patient Genetics Ancillary Study

Principal Investigator: [name], PhD Cedars-Sinai Medical Center, Los Angeles

Background and Rationale:

The outcome of HCV infection is determined by the interaction between the virus and the host immune response. The administration of interferon alpha in the treatment of chronic hepatitis C can have a direct antiviral effect and activate the immune system, resulting in elimination of the virus. Although response to interferon treatment differs depending on the viral load and viral genotype, it is not yet clear why different responses are observed in individuals with the same viral load and same genotype. It is likely that genetic constituents of the host may play an important role in viral clearance, disease outcome, and treatment response. However, the data on patient genetic studies are sparse, mostly focused on the HLA class I and class II genes, and the results have been inconsistent. We will test the hypothesis that host genetic factors contribute to treatment response and disease progression of HCV infected individuals. We will investigate the role of selected immunological genes involved in innate and adaptive, humoral and cellular immune

responses in treatment response, while considering the potential confounding effect of viral load, viral genotype, disease duration, and other non-genetic risk factors.

Study Aim:

To determine the contribution of patient genetic factors underlying responsiveness/non-responsiveness to antiviral therapy in African Americans and Caucasians. A lymphoblastoid cell line will be established to facilitate the proposed studies. We will test at least 22 candidate genes chosen on the basis of their role in interferon response and CD4+ (TH) type 1 and 2 responses using markers of 3.5KB density. Based on the significance level of associations, a minimum of 5 candidate genes will be further studied by fine mapping.

Study Endpoints:

- (a) Evaluate associations between the 22 (or more) candidate genes and non-response to anti-viral therapy by comparing gene frequencies in responders and non-responders.
- (b) Fine mapping of 5 (or more) candidate genes to identify specific genetic variants in the gene that determine therapeutic response/non-response.

Study Population:

N=400, all enrolled study participants

Additional 400 anti-HCV positive viremic patients from an external (to Virahep-C) NIDDK source. To further increase the study's power, and serve as an important control group, 50 anti-HCV positive non-viremic (resolved infection) patients obtained from [name] (Principal Investigator, Immunology Study, Portland VA Medical Center) will be tested. A separate consent form for genetic studies will be obtained from participants (See Appendix 4). Refusal to participate in the genetics study will not exclude patients from participating in the treatment trial or other ancillary studies.

Method for Analysis/Power Calculations:

To test the association between response to therapy and genetic markers, we will compare the response rate among different genotypic groups or between carriers and non-carriers. A Chi-square or exact test, or a Mantel-Haenszel test when data are stratified across levels of a potentially confounding factor, will be used to test association between genotype and phenotype. For quantitative phenotype (e.g. reduction of viral levels since the treatment), we will compare the mean difference or percent change between each genotype group (homozygous for allele 1, heterozygous, and homozygous for allele 2) or the allele carrier and the noncarrier groups. A one-way ANOVA or two-sample t-test (or a non-parametric equivalent, e.g., Wilcoxon's rank sum test) will be used to test the associations between genotype and phenotype. The tests we use will depend on the allele frequencies, trait distribution, and sample size in each group. If an allele's frequency is low, e.g. 10%, we may not have enough homozygotes for that allele, and as a result the comparison will be between two groups (carrier and non-carrier). If preliminary analysis indicates potential confounding, analysis of covariance, Mantel-Haenszel Chi-square statistics, or multiple logistic regression will be used to control for confounding. Since Caucasians and African Americans have different response rates to interferon/ribavirin therapy, the effect of each specific gene may be not be the same in these racial groups. Thus, we will first analyze data separately within each racial group. Subsequent analyses will be based on all subjects by either combining results from stratified analysis (Mantel-Haenszel Chi-square test) or through adjustment for race in multivariable modeling (e.g., multiple logistic regression).

Using Mantel-Haenszel statistics with strata defined by race, we estimated power for detecting various differences in the response rate between disease allele carriers and non-carriers in the 400 samples (200 Caucasians and 200 African Americans). The table below lists the power under three different situations: at 0.05 significance level without adjustment for multiple comparisons, at the 0.0005 level (comparison-wise type I error rate of 0.05 divided by 100, i.e., adjusting for 100 tests), and at the 0.00025 level (comparison-wise type I error rate of 0.05 divided by 200, i.e., adjusting for 200 tests). The disease allele frequency is assumed to be 10% in the HCV patient population. Overall, the power is >80% except when the difference of response rates between carriers and non-carriers is less than 20% in both Caucasians and African Americans and the Bonferroni correction is applied. These power calculations were based on assessing a qualitative variable of response to therapy (viral clearance). But we may also test response to therapy by using quantitative measures, such as reduction of viral levels since therapy.

Table	10
-------	----

	ican America	ins)	l, and 400 sa			
		ise Rate		Damada	Dama	
	ucasian		n American	Power1	Power2 ^b	Power3
Carrier	Non-carrier	Carrier	Non-carrier			
0.5	0.2	0.2	0.0	0.999	0.954	0.933
		0.3	0.0	1.000	0.996	0.994
		0.3	0.1	0.994	0.833	0.784
		0.4	0.1	0.999	0.971	0.957
0.5	0.3	0.2	0.0	0.960	0.590	0.519
		0.3	0.0	0.997	0.889	0.851
		0.3	0.1	0.905	0.417	0.348
		0.4	0.1	0.987	0.761	0.701
0.6	0.3	0.2	0.0	0.998	0.909	0.875
		0.3	0.0	1.000	0.989	0.982
		0.3	0.1	0.989	0.776	0.718
		0.4	0.1	0.999	0.950	0.929
0.6	0.4	0.2	0.0	0.951	0.552	0.480
		0.3	0.0	0.996	0.863	0.819
		0.3	0.1	0.896	0.397	0.329
		0.4	0.1	0.984	0.736	0.674

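### Table 10 (Patient Genetics) does not give the power of the race-stratified Mantel-Haenszel test it names, and its summary sentence contradicts its own entries

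*Protocol*

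**What the plan says.** Protocol section 8.2.2, under the power calculations, says: "Using Mantel-Haenszel statistics with strata defined by race, we estimated power for detecting various differences in the response rate" between carriers and non-carriers, "in the 400 samples (200 Caucasians and 200 African Americans"). The genetic input is: "The disease allele frequency is assumed to be 10% in the HCV patient population". For an allele this rare the same section expects that "we may not have enough homozygotes for that allele, and as a result the comparison will be between two groups (carrier and non-carrier"), so heterozygotes and homozygotes are pooled as carriers.

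Table 10 crosses four Caucasian pairs of response rates with four African American pairs (16 rows). Each row has three powers: one "at 0.05 significance level without adjustment for multiple comparisons", one at 0.0005 (0.05 divided by 100 tests) and one at 0.00025 (0.05 divided by 200). For Caucasian rates 0.5 v 0.3 and African American rates 0.2 v 0.0, for example, it prints "0.960 0.590 0.519".

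A summary sentence before the table says that power exceeds 80% in all cases but those where the carrier difference is under 20% in both races and the Bonferroni correction is applied.

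The section does not state the carrier share, the variance formula or any continuity correction.

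**The concern.** Apart from the carrier share, everything needed to check the table is stated, and the check fails. Many corrected powers look low for 200 patients per stratum with differences of 20 to 30 points. The summary sentence also describes an exception that no row of the table meets, while almost half of the corrected entries lie below 80%.

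The section plans to test at least 22 candidate genes and to take at least 5 to fine mapping on the significance level of their associations. Table 10 is the section's only statement of what such a screen can detect, with or without correction for multiple testing. A reader who relies on it gets the wrong detectable effects.

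**Working it through.** **Inputs.** Section 8.2.2 gives 200 per race, the three levels and the response rates by row. Carrier share is an assumption: under Hardy-Weinberg proportions 1 − 0.9² = 0.19, so a = 38 carriers and b = 162 non-carriers per race (n = 200). Two-sided critical values are 1.960, 3.481 and 3.662.

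**What the printed row implies.** For 0.5/0.3 with 0.2/0.0, add the critical value to the normal quantile of each printed power:
- 0.960: 1.751 + 1.960 = 3.711
- 0.590: 0.228 + 3.481 = 3.708
- 0.519: 0.048 + 3.662 = 3.710

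The three columns share one noncentrality of about 3.71. The levels were therefore applied consistently and two-sided.

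**What the named test gives, same row.** With w = ab/n = 38 × 162/200 = 30.78:
- Expected difference: Σw(p − q) = 30.78 × (0.2 + 0.2) = 12.312.
- Pooled rates: (38 × 0.5 + 162 × 0.3)/200 = 0.338 and (38 × 0.2)/200 = 0.038.
- Null variance: V0 = 30.78 × (0.338 × 0.662 + 0.038 × 0.962) × 200/199 = 8.053; square root 2.838.
- Variance under the alternative: V1 = 30.78² × (0.5 × 0.5/38 + 0.3 × 0.7/162 + 0.2 × 0.8/38) = 11.450; square root 3.384.
- Expected statistic: 12.312/2.838 = 4.34, against the 3.71 implied by the table.
- Power = Φ[(12.312 − z × 2.838)/3.384] = 0.977, 0.764 and 0.715.

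**Simulation of the test itself** (400,000 trials per row, 38 v 162 in each race, no continuity correction). These three rows contain the largest gaps. The exact column is the fully exact stratified test at the two corrected levels.

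| Caucasian | African American | Printed 0.05 / 0.0005 / 0.00025 | Simulated | Exact, 0.0005 / 0.00025 |
|---|---|---|---|---|
| 0.5/0.3 | 0.2/0.0 | 0.960 / 0.590 / 0.519 | 0.981 / 0.774 / 0.724 | 0.692 / 0.634 |
| 0.5/0.3 | 0.3/0.1 | 0.905 / 0.417 / 0.348 | 0.952 / 0.610 / 0.546 | 0.520 / 0.450 |
| 0.6/0.4 | 0.3/0.1 | 0.896 / 0.397 / 0.329 | 0.945 / 0.570 / 0.503 | 0.492 / 0.420 |

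Largest shortfalls of the printed values:
- at 0.05: 0.945 − 0.896 = 4.9 points
- at 0.0005: 0.610 − 0.417 = 19.3 points
- at 0.00025: 0.724 − 0.519 = 20.5 points

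With the usual 0.5 continuity correction, the first row gives 0.725 and 0.671 at the corrected levels, and the largest shortfalls over all rows are about 14 and 15 points. Drawing the carrier count at random instead of fixing it at 38 changes results by no more than a point.

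**Other readings tried.** A carrier share of 10% reverses the sign: the corrected columns would then be too high by up to about 21 to 22 points, and they still do not reproduce. Scanning carrier shares from 8% to 30%, the best single share (15%, continuity-corrected) still misses a cell by 5 points. Crude, allele-count, additive, log odds ratio, Woolf, risk-difference and arcsine versions do not reproduce the table either.

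**Summary sentence against the table.** This needs no genetic assumption. The smallest difference in any row is 20 points, so no row meets the stated exception. Printed values below 0.80:
- at 0.0005: 0.590, 0.417, 0.761, 0.776, 0.552, 0.397, 0.736 (7 rows)
- at 0.00025: 0.784, 0.519, 0.348, 0.701, 0.718, 0.480, 0.329, 0.674 (8 rows)

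Reading the exception as 20% or less does not rescue it: 0.761, 0.776 and 0.736 come from rows with a 30-point difference in one race. In the recomputed table without continuity correction, only the four rows with 20 points in both races stay below 0.80 at 0.0005. At 0.00025 one more joins them (0.6/0.4 with 0.4/0.1, 0.785).

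**The case against.** The strongest reply is that the table may be a conservative approximation at exactly these inputs. With 19% carriers, the null variance and a fixed deduction of about 1.58 from the summed count, the 0.0005 and 0.00025 columns come within 2.9 points and the 0.05 column within 0.6. But 1.58 is a fitted number about three times the usual 0.5, the section does not mention it, and it still does not reproduce every cell. Even the exact test, which is more conservative than the usual correction, has more power than printed in the three rows above.

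It is fair to say that the section names neither a variance formula nor a continuity correction, that it also allows exact tests, and that the carrier share is not given. In the text available the table's caption is cut and its footnotes are absent, and these might state an assumption. So the size of the error is conditional, and the authors should confirm what they used.

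Two stronger inferences are tempting. One is that the Bonferroni adjustment was done wrongly, because the gaps are large only in the corrected columns. The common noncentrality across columns rules this out; the 0.05 column carries the same fault, hidden by its nearness to 1. The other is that the low corrected powers steer the study towards the uncorrected level. Nothing in section 8.2.2 uses Table 10 to choose a level.

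**Conclusion.** Table 10 is wrong as a statement of the power of the named test at the stated inputs, in all three columns. On the natural reading of the allele frequency (Hardy-Weinberg, 38 of 200 carriers per race) it understates power by up to about 5, 19 and 20.5 points at 0.05, 0.0005 and 0.00025 without continuity correction. With the 0.5 correction the figures at the two stricter levels are about 14 and 15. The gap is largest where the difference is 20 points in both races. The direction depends on the carrier share; the failure to reproduce does not. The conflict between summary sentence and table stands under any carrier share.

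A reader might take 20 points as a flat shortfall, or conclude that the protocol overclaims. Neither follows: 20.5 is the largest cell under one variant, and on the literal reading the printed values are pessimistic. The genetics sample is all 400 enrolled participants, so the table sets no sample size, and no primary analysis rests on it. This is a minor correction.

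**What to change.** - Recompute all three power columns for the named race-stratified test, preferably by simulation, and replace the printed values.
- State beside the table the carrier share (or carrier count per race) derived from the 10% allele frequency, and whether a continuity correction is used. The authors should first confirm the share behind the printed figures.
- Reword the summary sentence so that its exceptions are the rows that fall below 80% in the corrected table.

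The cost is a short calculation, one table and one sentence. Patients, samples and the main trial analyses do not change.

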6.0 Data Analysis/Statistical Power

The study is designed to have 400 patients; 200 White/Caucasian, 200 Black/African American. There will be 80% power to detect a difference in the percentages of undetectable viral RNA 6 months following treatment (sustained virological response, SVR) between racial groups if the percentage of White/Caucasian patients with a SVR is 40% and the percentage in Black/African-American patients is 26% using a two-sided test with α = 0.05. In multivariable analyses, there will be 80% power to detect a difference if the percentages of SVR are 40% for Whites/Caucasians and 25% for Blacks/African Americans, assuming a multiple correlation coefficient of 0.4 between race and the other independent variables using a two-sided test with α = 0.05.

Primary analyses will be performed using all enrolled patients. Patients will be considered enrolled in the study upon taking the first dose of study medication. Participants who do not have outcome data will be included as treatment failures. We will also perform analyses that include only those participants with known outcome data.

Summary statistics will be generated to describe the study sample at baseline. Descriptive statistics, including measures of central tendency (e.g. means, medians) and estimates of spread (e.g., standard deviations) will be used for continuous variables such as age. Frequency distributions will be used for categorical variables such as education level. Ninety-five percent confidence intervals will be calculated for all point estimates of continuous data. Graphical displays (e.g. histograms, box plots) will also be used to describe the data. The baseline demographic information and viral characteristics of the racial groups will be compared using the chi-square test for association or exact tests for differences in proportions or trend in ordinal data. Continuous variables may be transformed, where appropriate, to meet the assumptions of parametric tests. The Student's t-test or a non-parametric alternative, the Wilcoxon rank-sum test, will be used to determine differences in the distribution of continuous data between the two racial groups.

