Method 3: Using a one-way analysis of variance (ANOVA) test to compare the distributions of the level of cytokine response to treatment among slow responders, fast responders and non-responders (i.e., 3 responder groups). Given a sample size of 72 subjects and using an alpha of 0.05, two-tailed test, we will have 80% power to detect an effect size of 0.38, corresponding to a large effect size for ANOVA.²⁹

Method 4: A t-test to compare the distributions of the level of cytokine responses between treatment responders (slow and fast responders combined) versus non-responders. Thus, these analyses are based on 2 responder groups. Given a sample of 72 subjects and using a two-tailed test with $\alpha = 0.05$, we will have 80% power to detect a difference in the mean level of cytokine response between treatment responders and non-responders equal to an effect size of 0.68 (approximately two-thirds of a standard deviation). According to Cohen, an effect size for a t-test of 0.7 would be in the medium-large range.

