Example of Method 2: Given a sample size of 200 Caucasians patients and assuming that one-third will be responders, we will have 80% power to detect an odds ratio of 1.6 for every one standard deviation increase from the mean number of cells that react, using a two-tailed test and $\alpha = 0.05$. This can be interpreted as saying that the odds of being a responder increases by 60% for every one standard deviation increase in the number of cells that react. Adjusting for potential confounders, and assuming a multiple correlation coefficient of 0.4 between the number of cells that react and the other independent variables, we will have 80% power to detect an odds ratio of 1.7.

CD8 Analyses

The number of CD8 cells showing response will be categorized using a clinically meaningful cutpoint. Then the proportion of responders showing greater than the cut-off value of cell responses will be compared to that of the non-responders. This comparison will be done within the racial groups.

Assuming α = 0.05, two-sided test, there will be 80% power to detect a difference if 60% of the responders show greater than the cut-off value of cell responses and 20%, or fewer of the non-responders do. This corresponds to an odds ratio of approximately 6.4. In multivariable analyses, there will be 80% power to detect a difference in proportions between 60% in the responders and 15% or less in the non-responders, using a two-tailed test with alpha equal to 0.05, and assuming a multiple correlation coefficient between the covariate of interest (e.g., responder) and the other independent variables. This corresponds to an odds ratio of about 8.5. These effects are large, however, it is expected that the differences will be substantial and that these are reasonable estimates.

12/08/03

Table 13

Study	Number of Patients	Patient Specifications	Specimen	Minimum Volume per Timepoint
Viral Genetics ([name])	400	Initially, the Viral Genetics study will include at least 96 patients based upon early response pattern and race	Plasma	2 ml (5 ml whole blood)
Viral Kinetics	400		Plasma	2 ml (5 ml whole blood)
Pharmacokinetics	400		Serum	3 ml (7 ml whole blood)
Patient Genetics ([name])	400	NA	Whole blood	15 ml
Interferon Signaling ([name])	All up to and including 4 wks, at least 72 at post- treatment	For 72 (or more), equal number with each early response pattern and race	Whole blood	16 ml

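### The Patient Genetics power summary contradicts its own Table 10 (15 of 32 Bonferroni-corrected cells are below 80%); one Interferon Signaling effect size and one CD8 odds ratio also need correcting

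*Protocol*

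**What the plan says.** **Patient Genetics (Protocol 8.2.2).** Power is for a Mantel-Haenszel comparison of allele carriers with non-carriers, stratified by race, "in the 400 samples (200 Caucasians and 200 African Americans"). Table 10 gives three powers per scenario. The first is "at 0.05 significance level without adjustment for multiple comparisons". The second applies a Bonferroni correction: "at the 0.0005 level (comparison-wise type I error rate of 0.05 divided by 100, i.e., adjusting for 100 tests"). The third uses 0.00025, which corrects for 200 tests. The text then concludes: "Overall, the power is >80% except when the difference of response rates between carriers and non-carriers is less than 20% in both Caucasians". The sentence goes on to name the other race and to limit this exception to Bonferroni-corrected tests.

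**Interferon Signaling (Protocol 8.2.3, Method 4).** A t-test compares slow and fast responders combined with non-responders. With 72 patients, 80% power is claimed for a mean difference "equal to an effect size of 0.68 (approximately two-thirds of a standard deviation"). The study population is at least six groups of 12: three response patterns in each of two races.

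**Immunology (Protocol 8.2.4, CD8 Analyses).** For 60% of responders versus 20% of non-responders above the cut-off, the protocol adds: "This corresponds to an odds ratio of approximately 6.4".

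**The concern.** The summary sentence tells the reader which genetic effects the study can detect after correction for multiple testing. As worded, a 20-point difference in response between carriers and non-carriers is detectable with more than 80% power even at 0.0005 and 0.00025. The table below it shows power as low as 0.329 for such differences. Anyone who relies on the sentence and not the table would overestimate what the candidate-gene screen can find at the corrected levels.

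The other two figures are local. The Method 4 effect size does not match the planned group sizes, and the CD8 odds ratio does not follow from the two percentages beside it.

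**Working it through.** **1. Sentence against table**

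Inputs: the 16 rows of Table 10. The difference in each race is the carrier rate minus the non-carrier rate, for example 0.5 − 0.3 = 20 points and 0.4 − 0.1 = 30 points. Every row has 20 or 30 points in each race, so no row meets the stated exception of less than 20 in both.

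Grouping the printed powers by the pair of differences:

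| Differences in the two races | Rows | Power at 0.05 | Power at 0.0005 | Power at 0.00025 | Corrected cells below 0.80 |
|---|---|---|---|---|---|
| 20 and 20 | 4 | 0.896–0.960 | 0.397–0.590 | 0.329–0.519 | 4 + 4 = 8 of 8 |
| 30 and 20 (either way) | 8 | 0.984–0.999 | 0.736–0.954 | 0.674–0.933 | 3 + 4 = 7 of 16 |
| 30 and 30 | 4 | 0.999–1.000 | 0.950–0.996 | 0.929–0.994 | 0 of 8 |
| All | 16 | 0.896–1.000 | 0.397–0.996 | 0.329–0.994 | 7 + 8 = 15 of 32 |

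The uncorrected column supports the sentence throughout. The corrected columns do not.

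If the exception is read as 20 points or less in both races, the four 20-and-20 rows (8 cells) are excused. Then 15 − 8 = 7 cells still conflict: 0.784; 0.761 and 0.701; 0.776 and 0.718; 0.736 and 0.674.

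**2. Can Table 10 itself be reproduced?**

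Not exactly. The protocol states an allele frequency ("The disease allele frequency is assumed to be 10% in the HCV patient population") but no carrier share. Hardy-Weinberg proportions, an assumption, give 1 − 0.9² = 19% carriers. No variance form or carrier share tried matched every cell within 2 points. Simulating the stratified test with 19% carriers left 9 of 32 corrected cells below 0.80 without a continuity correction and 12 of 32 with one. The contradiction does not depend on this, because it sets the sentence against the printed cells.

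**3. Interferon Signaling, Method 4**

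Six groups of 12 give 2 × 12 = 24 non-responders and 4 × 12 = 48 slow or fast responders. The noncentrality is d × √(n₁n₂/(n₁+n₂)), with 70 degrees of freedom and a two-sided 5% critical value of 1.994.

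- Stated d = 0.68, 24 vs 48: 0.68 × √16 = 2.72, power 76.5% (77.6% by normal approximation).
- d = 0.71, 24 vs 48: 0.71 × 4 = 2.84, power 80.0%.
- d = 0.68, 36 vs 36: 0.68 × √18 = 2.885, power 81.2%.

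The stated 0.68 therefore reaches 80% with an equal split, which is not the planned one.

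**4. CD8 odds ratio**

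(0.60/0.40) ÷ (0.20/0.80) = 1.5 ÷ 0.25 = 6.0. An odds ratio of 6.4 corresponds to 19%: 1.5 ÷ (0.19/0.81) = 6.39. The companion value for 60% versus 15% is right: 1.5 ÷ (0.15/0.85) = 8.5.

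**The case against.** **For leaving it alone.** The correct powers are printed directly under the sentence, and the likely slip is writing less than 20 for 20 or less. That excuses eight cells but not the other seven. To reconcile everything one would also have to read both races as at least one race, which the text does not say. Method 4 is only 3.5 points short; its last sentence rounds the effect to 0.7, and 72 is a minimum. The CD8 text says approximately, and 20% or fewer. All this limits the seriousness, but the figures remain wrong as stated.

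**Stronger readings that the protocol does not support:**

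- *Table 10 is optimistic.* With 19% carriers, its African American scenarios imply overall response of 0.19 × carrier rate + 0.81 × non-carrier rate = 3.8%, 5.7%, 13.8% or 15.7%, whereas Section 6.0 assumes "the percentage in Black/African-American patients is 26" percent. But the 19% is an unstated assumption, and Section 8.2.4 also plans for 15% response in African Americans. At overall rates of 40% and 26% with 20 points in each race, stratified power is about 0.90–0.92, 0.40–0.46 and 0.33–0.39 at the three levels. That is close to the printed 20-and-20 rows with African American rates of 0.3 and 0.1 (0.905/0.417/0.348 and 0.896/0.397/0.329). Optimism is not shown.
- *The ancillary power figures fail generally.* They do not. The Viral Genetics comparison of 35% versus 10% gives 84.6%; the chi-square effect sizes 0.32 and 0.37 give 80.8% and 80.9%; Methods 2 and 3 give 83.8% and 81.3%; Table 11 recomputes to 0.754, 0.861 and 0.854 against 0.76, 0.86 and 0.86; Table 12 fits the logistic formula that it cites; and the CD8 power itself is 84.5% (78.8% by Fisher's exact test).
- *The error drove the design, or a null gene result will be read as no effect.* The genetics sample is all trial participants, so Table 10 did not set it. External samples are to be added. Genes go forward to fine mapping on significance, with no stated corrected threshold, and Section 6.0 uses 0.05 for all analyses, where every row is at least 0.896. Nothing says how a null result would be read.

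**Conclusion.** The summary sentence in Section 8.2.2 is wrong on its own table: 15 of 32 corrected cells contradict it as worded, and 7 on the most generous reading of its exception. This needs only the printed rows. The Method 4 effect size is too small for 24 versus 48, which assumes the minimum of 12 per group and a two-sided 5% t-test. The CD8 odds ratio is an arithmetic slip with no bearing on that study's power. The correction is moderate to minor and confined to ancillary studies. It leaves the primary SVR comparison untouched: 40% versus 26% with 200 per group gives 84.8% power, above the stated 80%.

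**What to change.** - **Section 8.2.2:** replace the summary sentence with wording such as: without correction, power is at least 0.896 in all scenarios; after Bonferroni correction it is 33–59% when the difference is 20 points in both races, 67–95% when it is 30 points in one race and 20 in the other (below 80% in 7 of 16 cells), and at least 0.929 when it is 30 points in both.
- **Section 8.2.3, Method 4:** restate as 80% power for an effect size of about 0.71 with 24 non-responders and 48 responders.
- **Section 8.2.4, CD8 Analyses:** change the odds ratio for 60% versus 20% to 6.0.

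The cost is three text edits. No sample size, procedure or analysis changes; the stated power for the genetics study simply becomes less favourable.

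### The summary sentence above Table 10 claims more than 80% power outside an exception that no row of the table meets, while 7 (100 tests) and 8 (200 tests) of its 16 rows fall below 80%

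*Protocol*

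**What the plan says.** Section 8.2.2 gives the setting in the paragraph above Table 10. The test is described as "Using Mantel-Haenszel statistics with strata defined by race", and power is given "in the 400 samples (200 Caucasians and 200 African Americans". Three situations are tabulated:

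- Power1: "at 0.05 significance level without adjustment for multiple comparisons".
- Power2: "at the 0.0005 level (comparison-wise type I error rate of 0.05 divided by 100, i.e., adjusting for 100 tests".
- Power3: "at the 0.00025 level (comparison-wise type I error rate of 0.05 divided by 200, i.e., adjusting for 200 tests".

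On allele frequency the section says: "The disease allele frequency is assumed to be 10% in the HCV patient population". It gives neither the resulting share of carriers nor the variance formula.

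The same paragraph then draws its conclusion: "Overall, the power is >80% except when the difference of response rates between carriers and non-carriers is less than 20% in both Caucasians". The remainder of that sentence asks the same of the other race and limits the exception to Bonferroni-corrected tests. Table 10 crosses four Caucasian response-rate pairs with four African American pairs, making 16 rows.

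**The concern.** The exception has two conditions that must hold together: Bonferroni correction, and a difference under 20 points in both races. Anything outside it is said to have more than 80% power, including a 20-point difference in both races after correction. The table directly below appears to give much lower values for exactly that case. If so, the text summary of what this study can detect after multiplicity correction is wrong in the favourable direction. The section plans to test at least 22 candidate genes with dense markers, so the corrected columns are not incidental.

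**Working it through.** **Inputs.** All come from section 8.2.2 and Table 10. The Caucasian pairs (carrier, non-carrier) are 0.5/0.2, 0.5/0.3, 0.6/0.3 and 0.6/0.4, with differences of 30, 20, 30 and 20 points. The African American pairs are 0.2/0.0, 0.3/0.0, 0.3/0.1 and 0.4/0.1, with differences of 20, 30, 20 and 30 points.

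**Step 1: does any row meet the exception?** The smallest difference in either race is 20 points. Rows with less than 20 in both races: 0 of 16. The sentence therefore implies more than 80% in all 48 power cells.

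**Step 2: count printed cells below 0.80.**

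| Difference in the two races | Rows | Below 0.80, Power1 | Below 0.80, Power2 (0.0005) | Below 0.80, Power3 (0.00025) |
|---|---|---|---|---|
| 30 and 30 | 4 | 0 | 0 (lowest 0.950) | 0 (lowest 0.929) |
| 20 in one, 30 in the other | 8 | 0 | 3 (0.736 to 0.776) | 4 (0.674 to 0.784) |
| 20 and 20 | 4 | 0 | 4 (0.397 to 0.590) | 4 (0.329 to 0.519) |
| All | 16 | 0 (lowest 0.896) | 7 | 8 |

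**Step 3: try the charitable reading.** Suppose the exception was meant as 20 points or less in both races. It then excuses the four 20/20 rows only. These mixed rows still fail (Power2, Power3):

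- 0.5/0.3 with 0.4/0.1: 0.761, 0.701
- 0.6/0.3 with 0.3/0.1: 0.776, 0.718
- 0.6/0.4 with 0.4/0.1: 0.736, 0.674
- 0.5/0.2 with 0.3/0.1: 0.833, 0.784 (fails at 0.00025 only)

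So the condition that both races be affected is wrong as well as the inequality.

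**Step 4: are the low values text-extraction errors?** If the three columns share one calculation, the shift Φ⁻¹(power) + z(1 − α/2) should be the same in each, with z = 1.960, 3.481 and 3.662. For 0.5/0.3 with 0.3/0.1 the printed powers 0.905, 0.417 and 0.348 give 3.271, 3.271 and 3.272. For 0.6/0.4 with 0.3/0.1 they give 3.219, 3.220 and 3.220. The columns agree with one another, so the low values are as calculated by the authors.

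**Step 5: can the cells be reproduced?** I used a two-stratum Mantel-Haenszel normal approximation, two-sided, without continuity correction. With w = n₁n₂/n in each stratum, shift = Σw(p₁ − p₂)/√V and power = Φ(shift − z). V is either Σw²[p₁(1 − p₁)/n₁ + p₂(1 − p₂)/n₂] (alternative) or Σw·p̄(1 − p̄)·n/(n − 1) (null). The carrier share is my assumption: 19% follows from a 10% allele under Hardy-Weinberg, and I tried 10% to 21%.

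Example, 0.6/0.4 with 0.3/0.1, 20% carriers, alternative variance: n₁ = 40, n₂ = 160, w = 32. The numerator is 32 × (0.2 + 0.2) = 12.8. V = 1024 × (0.006 + 0.0015 + 0.00525 + 0.0005625) = 13.63. The shift is 12.8/3.692 = 3.467, and power at 0.0005 is Φ(3.467 − 3.481) = 0.494, against 0.397 printed.

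Some rows match closely: 0.5/0.3 with 0.2/0.0 gives 0.595 against 0.590. Over all corrected cells, the largest miss with alternative variance is 9.7 points at 20% carriers and 10.7 at 19%. With null variance at 19% it is 23.2. In every variant tried, at least 3 rows (0.0005) and 4 rows (0.00025) fall below 80%. The mixed rows are more sensitive: with null variance and 20% or 21% carriers, none of them falls below 80%.

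**The case against.** The strongest defence is that nothing is hidden. Table 10 prints every value just below the sentence, and its uncorrected column agrees with it. The sentence also covers only the 400 trial samples, while section 8.2.2 adds 400 external viremic patients and 50 with resolved infection, and allows quantitative phenotypes. The sample size is fixed by the main trial. These points limit the consequence, and they stand. They do not make the sentence true: a correct table does not cure a false summary of it.

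Three stronger readings are tempting but not supported:

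- **That the table is sound and only the sentence is wrong.** Step 5 does not show this. Without the carrier share and variance formula, the cells can be neither confirmed nor rejected.
- **That half the rows fail after correction.** This is exact at the 0.00025 level. At 0.0005 it is 7 of 16.
- **That a negative screen would be taken to exclude 20-point effects.** The protocol does not make Bonferroni the decision rule. Section 8.2.2 lists it as a power situation and selects genes for fine mapping on the significance of their associations, and section 6.0 uses p < 0.05 for all analyses. How a null result would be read is conjecture.

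**Conclusion.** The sentence is wrong as written, because the table it summarises contradicts it. At 20 points in both races the sentence implies more than 80% power after correction, and the table prints 33% to 59%. With 20 points in one race and 30 in the other, 3 of 8 scenarios (100 tests) or 4 of 8 (200 tests) are also short, at 67% to 78%. With 30 points in both, the claim holds.

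This conclusion rests on the text and the printed table alone and needs no assumption about carriers or variance. The size of the shortfall is that of the printed cells and could move if they are recalculated, most of all in the mixed rows. The point is confined to an ancillary study. It has no bearing on the primary SVR comparison, the main trial's sample size or its conduct.

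**What to change.** Replace the summary sentence with one that matches the table, for example:

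> Without correction, power is at least 89% in all scenarios shown. With Bonferroni correction, power exceeds 80% in all scenarios with a 30-point difference in both races (at least 92%), is 33-59% with 20 points in both, and falls to 67-78% in 3 (100 tests) or 4 (200 tests) of the 8 scenarios with 20 points in one race and 30 in the other.

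Before finalising it, state the carrier share and variance formula used for Table 10 and recheck the cells. If any change, take the figures in the sentence from the corrected table.

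The cost is one sentence, a short note on method and a rerun of 16 scenarios. The stated power becomes less favourable. No change to enrolment, sampling or analysis follows.
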